3.6.9. Secondary Endpoints

The first secondary endpoint is the differential measurement of red, green, and blue levels in VS tissue compared to the facial nerve and cochlear nerve using FS and YE560. ImageJ software will be used to analyze representative images capture from microsurgery. The operating surgeon will delineate regions of interest for the VS, facial nerve, and cochlear nerve. Separate similar analysis will be performed for other tumor types.

The second secondary endpoint will include gross total resection rate, postoperative facial nerve function, and postoperative hearing status. Facial nerve function will be assessed by clinical evaluation at 3 month postoperative visits as well as intraoperative supramaximal stimulation and minimum stimulation levels as routinely performed in surgery.

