1.3. Purpose

The purpose of this study is:

- To evaluate the benefit of using intravenous fluorescein sodium (FS) and YELLOW 560 nm microscope filter (YE560) during surgery for vestibular schwannomas (VS) menioma, head and neck paraganglioma (HNP), or head and neck schwannoma (HNS)
- To determine the optimum FS dose and timing to be used with the YE560 device

VSs are benign, slow-growing neoplasms of the myelin-containing Schwann cells of the vestibular division of the vestibulocochlear nerve. These tumors are in close proximity to the facial nerve and cochlear division of the vestibulocochlear nerve. These nerves allow for facial movement and hearing, respectively. Management of these indolent tumors has shifted to more conservative means of minimizing growth and maintaining facial function and hearing. Management of VSs includes observation with serial MRI exams, stereotactic radiosurgery, and microsurgery.

Similarly, HNP, HNS and skull base meningiomas are benign but infiltrative tumors that grow adjacent to important neurovascular structures including, the cranial nerves. These tumors can be observed, treated with radiosurgery, or microsurgery based on size, symptoms, and patient preference.

When microsurgical resection of VS, schwannomas, meningiomas, or paragangliomas is performed, distinguishing the tumor from healthy nerve tissue is performed via direct visualization under light microscopy and tissue manipulation. Often, these tumors are intimately associated with the surrounding nerves, and can be difficult to distinguish under the microscope. In many cases intraoperative cranial nerve monitoring allow for the use of a stimulation probe to help make this distinction.

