3.4. Hypothesis

12. Given prior evidence of preferential uptake of FS in VS and meningiomas due to disrupted blood brain barrier, we hypothesize that use of intravenous FS will allow for visual differentiation of tumor and surrounding structures and nerves using YE560.
13. The optimal dosing for FS has not been established for this application. Pedro et al utilized 0.5-1.0 mg/kg body weight to visualize peripheral nerve sheath tumors with YE560. The authors found saturation of all tissues with 3-4 mg/kg dose within 18 seconds of administration. The blood-brain barrier may play a modulating role. Schebesch et al (2013) used 3-4 mg/kg to visualize malignant gliomas and observed fluorescence after 20-30 minutes. We suspect that the optimal dose will be 3-4 mg/kg, and peak fluorescence will take a similar amount of time. However, we will initially utilize 1.0 mg/kg SF administered at the time of first visualizing the tumor to enable subsequent doses (up to a maximum of 500 mg or 7 mg/kg). This will allow us

to determine the minimum effective dose and observe the time to peak fluorescence. The optimal dosing strategy will be finalized after the first 10 cases.

14. We hypothesize that the surgeons will be satisfied with the use of SF and YE560, as reflected in responses on the Surgeon Survey. Specifically, we hypothesize that greater than 75% of surgeons would choose to use SF and YE560 at least in the majority of future VS, meningioma, HNP, or HNS resections based on responses from the Surgeon Survey. Secondarily, we hypothesize that surgeons will rate the correlation of fluorescence with visual assessment with white light microscopy and electrostimulation to be “good” or “excellent” for over 75% of the cases.
15. Because the yellow fluorescence is primarily comprised of red and green components, we hypothesize that RGB component analysis of intraoperative images will yield significantly higher red and green values in the VS compared to the facial and cochlear nerves. Similar analysis may be conducted between the tumor and surround nerves or structures of interest for meningiomas, HNP, and HNS.

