3.5. Design and Proposed Analysis

16. The feasibility study will involve 90 patients, focusing on intra-operative visualization of fluorescein using YE560 in VS, meningioma, HNP, or HNS, inclusive of recurrent tumors, previously radiated tumors, and patients with neurofibromatosis type 2. There will be an allowance to enroll up to 95 patients to meet the goal of 90 subjects if subjects are withdrawn from the study due to a different pathologic entity diagnosed on biopsy of the tumor. Establishing the optimal dose and timing for FS will be a part of the feasibility study. Flexibility will be allowed with the dose and timing to achieve optimal visualization condition based on surgeon feedback with a maximum cumulative dose of 500 mg (standard dosage for ophthalmology angiography). The study will be largely descriptive, documenting the macroscopic appearance of FS and describing surgeon observations with regards to timing of peak fluorescence, correlation with electrostimulation, and utility in differentiating normal tissue from tumor.
17. Images containing the tumor and facial and cochlear nerves (or other relevant structures of interest in the case of meningioma, HNP, or HNS) will be captured with the microscope with the YE560 filter by the surgeon and analyzed; the YE560 filter will then be turned off and another identical image will be captured under white light microscopy for the separate survey validation analysis. For the RGB component image analysis, the fluorescence of the tumor will be measured in comparison to the facial nerve and cochlear nerve using ImageJ image analysis software to quantify the red, green, and blue components of the images. Inferential statistics will be used to compare the red, green, and blue components of regions of interest from the VS and the adjacent facial or cochlear nerve.
18. For the survey validation analysis, we will validate the question “How well did fluorescence correlate with your visual assessment of the tumor and nerve tissue under normal microscopy without the Yellow 560 filter?” The neurosurgeons and neurologists will be presented with 30-60 second videos of the VS and facial and/or cochlear nerves, with and without YE560 active. The surgeons will respond to the above question with choices of “no correlation,” “some

correlation,” “good correlation,” and “excellent correlation.” Other questions from the surgeon survey will not be validated due to the scope of the feasibility study.

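### RGB endpoint: the operating surgeon, who has seen the fluorescence, outlines tumour and nerve with nothing keeping the outlines independent of the brightness compared, so the contrast is open to upward bias

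*Protocol*

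**What the plan says.** Protocol section 3.6.9 makes the tumour-versus-nerve difference in red, green and blue the first secondary endpoint and names the person who draws the regions: "The operating surgeon will delineate regions of interest for the VS, facial nerve, and cochlear nerve". Other tumour types get a similar separate analysis.

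Section 3.5 (item 17) says the images for this analysis "will be captured with the microscope with the YE560 filter by the surgeon and analyzed". The filter is then switched off and "another identical image will be captured under white light microscopy for the separate survey validation analysis". Section 3.6.11 (item 4) repeats that each capture event yields a YE560 and a white-light image, and item 6 has the time of greatest differential fluorescence documented in the surgeon's survey.

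For the analysis, section 3.5 states: "Inferential statistics will be used to compare the red, green, and blue components of regions of interest". The hypothesis in section 3.4 (item 15) is directional: "RGB component analysis of intraoperative images will yield significantly higher red and green values in the VS compared to the facial and cochlear nerves".

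On how separable the tissues are, section 1.3 says: "Often, these tumors are intimately associated with the surrounding nerves, and can be difficult to distinguish under the microscope". It adds: "In many cases intraoperative cranial nerve monitoring allow for the use of a stimulation probe to help make this distinction".

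**The concern.** The quantity tested is brightness, and the regions that define it are drawn by someone who has already seen which tissue is bright. Where anatomy settles the label this does no harm. Where tumour and nerve adhere, an observer who knows the fluorescence can let it decide which pixels count as tumour. The comparison is then partly circular, and the error runs only towards a brighter tumour.

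At stake is the one quantitative test of tissue differentiation in the study. The interface is also where the filter is hoped to be most useful, so bias there bears on the part of the result that readers will care about most.

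**Working it through.** **Reading the text.** The protocol gives no alpha, SD, effect size or sample-size argument for this endpoint, so there is no planned figure to reproduce. Four questions can be put to it:

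- *Who outlines?* The operating surgeon (3.6.9). No second or masked reader is named.
- *Has that person seen the fluorescence?* Yes (3.5 item 17; 3.6.11 item 6).
- *On which image is the outline drawn?* Not stated. Measurement is on the YE560 image. The white-light still is given to survey validation. Item 18 of section 3.5 runs that validation on videos (surgeons "will be presented with 30-60 second videos of the VS and facial and/or cochlear nerves"), while section 3.6.8 speaks of images. Neither bars use of the still for outlining.
- *Is there an independent anchor?* In part. The surgeon knows the anatomy, a stimulation probe helps in many cases (1.3), the facial nerve is stimulated after resection (3.6.11 item 9), and survey question 8 rates fluorescence against stimulation. None of these is made a rule for placing regions. The only stimulation procedure described in detail is for the facial nerve, yet the cochlear nerve is also a comparator.

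**Illustration of direction and size.** Every input here is an assumption. Per case, the tumour mean is N(δ, 1), the nerve mean is N(0, 1), and each region has 10 patches with added N(0, 1) noise. A share *a* of each region is interface. In a fraction *f* of cases the interface patches of both regions are pooled and the brighter half is called tumour; everything else is labelled correctly. The case contrast D is the mean of tumour-labelled patches minus the mean of nerve-labelled patches. The test is t = mean(D) / (SD(D)/√n), two-sided 5%, with 8,000 simulated trials per cell. Because the 90 patients span four tumour types, n is taken as 30, 45 or 90 pairs.

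No true contrast (δ = 0):

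| a | f | Mean contrast (SD) | Rejection, n = 30 / 45 / 90 |
|---|---|---|---|
| 0.2 | 0 | 0 | 5.1 / 4.5 / 5.3% |
| 0.2 | 0.2 | 0.07 | 5.8 / 6.1 / 7.0% |
| 0.2 | 0.5 | 0.17 | 10.0 / 13.4 / 23.1% |
| 0.5 | 0.2 | 0.19 | 12.0 / 15.2 / 24.2% |

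True contrast present, a = 0.2. A fully sorted case averages 0.753, 1.18 or 2.08 at δ = 0.5, 1 or 2. The trial mean is (1 − f)δ + f × (sorted mean):

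- f = 0.2: 0.8×0.5 + 0.2×0.753 = 0.55; 0.8×1 + 0.2×1.18 = 1.04; 0.8×2 + 0.2×2.08 = 2.02. Bias 0.05, 0.04, 0.02 SD.
- f = 0.5: 0.63, 1.09, 2.04. Bias 0.13, 0.09, 0.04 SD.

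A rerun with a different seed agreed to within simulation error.

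**A different model.** If the reader instead takes the brightest of 2 to 5 tumour patches and the dimmest of 2 to 5 nerve patches in 25% of cases, a null contrast becomes 0.28 to 0.58 SD, with rejection of 18–45% at n = 30. The direction is the same and the size is very different, so the size depends on the model chosen.

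**The error on the other side.** Suppose white-light labelling of the interface is no better than chance in an affected case (a worst case). The interface then contributes nothing and the contrast is (1 − a)δ = 0.8δ:

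| δ | Sorted by brightness | White light at chance |
|---|---|---|
| 0.5 | 0.75 (+0.25) | 0.40 (−0.10) |
| 1 | 1.18 (+0.18) | 0.80 (−0.20) |
| 2 | 2.08 (+0.08) | 1.60 (−0.40) |

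At δ = 0 the white-light contrast stays at 0 and rejection stays near 5%.

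**Hard cases.** If 20% of cases are hard with a true contrast of 0.5 and the rest have 1, the truth over all cases is 0.8×1 + 0.2×0.5 = 0.90. Leaving the hard cases out gives 1.00. Including them outlined on YE560 gives 0.8×1 + 0.2×0.753 = 0.95. Both exceed 0.90.

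**The case against.** The strongest reply is that the protocol fixes only who draws the regions, and that the choice is sensible: the operating surgeon saw the anatomy and the stimulation responses. The image used and the placement rule could sit in an SAP or imaging manual that is not shown. This stands in part. A reader might infer that the protocol has regions drawn on the YE560 image or by brightness; no section says so. A reader might also infer that the nerve label has no anchor but fluorescence; sections 1.3 and 3.6.11 show otherwise. What remains is that the protocol names an unmasked reader and gives the obvious safeguard, the paired still, to another analysis. A later document merely consistent with that would keep the problem.

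Second, the size is unanchored, and small when the true contrast is 1 to 2 SD, while the protocol cites preferential uptake. This stands in full.

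Third, section 1.3 describes difficulty under ordinary microscopy, so white-light outlines will also err. This stands as a cost. It does not defeat the change, because that error dilutes the contrast and leaves the false-positive rate at its nominal level, whereas sorting by brightness inflates both.

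Fourth, results with and without the hard cases do not bracket the truth. The hard-case example confirms this, and the fix is worded accordingly.

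**Conclusion.** The concern holds as an exposure to upward bias in the first secondary endpoint, confined to tissue that is hard to assign. It does not establish that bias will occur, and a positive RGB result could not be dismissed as an artefact on this ground. The illustrative range runs from 0.02 SD (large true contrast, few cases affected) to 0.19 SD (no true contrast, half of each region at the interface). It rests wholly on assumed interface shares, affected fractions and patch noise. The bias is probably small where the true contrast is large and matters most where it is small or absent, which is the situation a test of hypothesis 15 must guard against.

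The study is a mainly descriptive feasibility study and the primary survey outcome is untouched. The change is worth making because it uses images already planned; it is not a reason to hold the study.

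**What to change.** In sections 3.5 and 3.6.9, state that:

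1. The operating surgeon outlines tumour and nerve on the paired white-light still from section 3.6.11 item 4, without the YE560 image in view, using stimulation results where available.
2. The regions are transferred unchanged to the matching YE560 image for ImageJ measurement, and this is the main RGB analysis.
3. Cases that cannot be labelled under white light, or whose image pairs do not align, are counted, described and reported separately as outlined on YE560. If they are added in a sensitivity analysis, the two results are not presented as bounds on the truth.

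Cost: no new procedure, staff or data, but effort to align image pairs. The surgeon's recall of the fluorescence is reduced, not removed. The main result describes only cases that can be labelled under white light. Mislabelling at the interface can pull the contrast towards zero, which is conservative for hypothesis 15.

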3.1. Objectives

Primary objective of this initial feasibility study is to evaluate the benefit of using YE560 to visualize fluorescein sodium (FS) during surgery of VS, Meningioma, HNP, or HNS, determined from surgeon assessment.

Secondary objectives are:

- To evaluate the optimum FS dose and timing to be used with the YE560 device as determined by reported performance on surgeon surveys
- Quantify tissue differentiation of fluorescent VS and adjacent nerves using RGB image analysis
- To report clinical outcomes, including GTR rates, postoperative hearing outcomes, and postoperative facial nerve function

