3.6.5. Inclusion Criteria

Inclusion criteria shall be:

- Patient with a suspected VS, meningioma, HNP or HNS
- Recurrent VS, meningioma, HNP, or HNS with prior microsurgical resection or radiation therapy
- Clinical indication for microsurgical resection

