9. Following completion of tumor resection and prior to closing of the dura, supramaximal and minimum stimulation values will be obtained (if relevant), as is standard practice with vestibular schwannoma microsurgery at our institution. The process is as described in Schmitt et al. (2013). In brief, transcutaneous bipolar electrodes are used at the extratemporal main trunk of the facial nerve to stimulate the nerve at 100 msec pulses increasing from 0 mA until a plateau amplitude compound muscle action potential is obtained. A Prass probe is used to stimulate the facial nerve proximal to the tumor (at the brainstem if possible) at increasing current (starting at 0 mA) until a plateau of CMAP is obtained. The ratio of these amplitude responses is calculated and subtracted from 1 to calculate the supramaximal stimulation. The minimum stimulation is the minimum current level at which a reliable facian nerve response can be obtained with proximal stimulation of the facial nerve using the Prass probe.

11. Suspected lesions that are found to be a histopathological entity excluded from this study after microsurgical resection and biopsy will be withdrawn from the study.

12. Post-procedure data analysis will include analysis of surgeon survey responses and, red/green/blue component analysis using ImageJ software. Additional data (demographics, imaging characteristics, facial nerve and audiometric data) will be reviewed and recorded from preoperative and 3 month postoperative visits. Video recordings will be edited to 30-60 second videos following the case with

representative views of the VS, facial nerve and cochlear nerve with and without the YE560 active. These edited videos will be used for the aforementioned surgeon validation study rating the correlation of fluorescence with white light microscopy.

13. Upon completion of surgery, operating surgeons will complete the remainder of the paper survey (Appendix 3). The surveys will be collected, with responses logged in the Rave database. The paper surveys will be stored in a secure location in the Otolaryngology department.

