7.4. Subject Compliance and Adverse Event Monitoring

7.4.1. Adverse Event Monitoring

Adverse events (AEs) must be reported on the Adverse Event Form (AEF). Adverse events that will be monitored include urticaria, anaphylaxis, respiratory compromise, cardiac events, seizure, and death. These events will be monitored in the first 3 months after surgery. Complete clearance of SF is expected within 72 hours, and associated adverse events, if any, are anticipated within that timeframe. After discharge from the hospital, any reporting of adverse events will rely upon participants contacting the research team prior to the scheduled 3 month follow up. Nausea and vomiting will not be included as an adverse event as these symptoms are expected outcomes from surgery.

If adverse events occur, the first concern will be the safety and welfare of the patient. Appropriate medical intervention will be made. Any adverse events observed by the Investigator or reported by the patients will be recorded in the appropriate section of the patient's Case Report Form (CRF) as well as on an Adverse Event Form.

The Investigator must categorize each AE by degree of harm to the patient (mild, moderate, or serious), and the relationship to study device (not related, possibly, probably, or definitely) in the Adverse Event Form. Adverse events observed will be captured on the Adverse Event Follow-up Form and the CRF until such time the adverse event is reported as resolved, or for the course of the study if the event does not resolve.

A serious adverse event includes any prolong hospitalization, and any event that is life-threatening, results in permanent impairment of a bodily function or permanent damage to a body structure, or an event that necessitates medical or surgical intervention to preclude such permanent impairment or permanent damage.

Changes in any chronic condition or disease that are consistent with natural disease progression are not considered AEs and will not be recorded on an AE CRF.

Medical treatment related to any adverse events will not be paid for by the study, Mayo Clinic, or the Sponsor. Patients and their insurance will be billed for any treatments or encounters associated with an adverse event.

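### The functional secondary endpoint covers only facial nerve and hearing for all four tumor types, so other cranial nerves beside a meningioma, paraganglioma or non-vestibular schwannoma have no planned measure

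*Protocol*

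**What the plan says.** **Who is enrolled.** The first inclusion criterion in section 3.6.5 is "Patient with a suspected VS, meningioma, HNP or HNS". Sections 3.5 and 3.6.2 also describe 90 patients drawn from all four tumor types.

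**What lies near the added tumors.** Section 1.3 describes HNP, HNS and skull base meningioma as "benign but infiltrative tumors that grow adjacent to important neurovascular structures including, the cranial nerves".

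**Which function is measured.** The secondary objective in 3.1 is "To report clinical outcomes, including GTR rates, postoperative hearing outcomes, and postoperative facial nerve function". Section 3.6.9 gives the matching endpoint: "The second secondary endpoint will include gross total resection rate, postoperative facial nerve function, and postoperative hearing status". Section 3.6.11 lists what is collected: "Additional data (demographics, imaging characteristics, facial nerve and audiometric data) will be reviewed and recorded from preoperative and 3 month postoperative visits". None of the three names another cranial nerve or varies by tumor type.

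**Where the plan does adapt.** Section 3.5 extends image capture to structures other than the facial and cochlear nerves: "or other relevant structures of interest in the case of meningioma, HNP, or HNS". The RGB paragraph of 3.6.9 adds: "Separate similar analysis will be performed for other tumor types".

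**Safety.** Section 7.4.1 reads: "Adverse events that will be monitored include urticaria, anaphylaxis, respiratory compromise, cardiac events, seizure, and death". Cranial nerve deficit is not on this list.

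**The concern.** Facial function and hearing suit vestibular schwannoma (VS), whose closeness to the facial and cochlear nerves is set out in 1.3. The same pair of outcomes is carried over unchanged to three tumor types for which the protocol itself points to the cranial nerves more broadly.

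The study asks whether fluorescence helps the surgeon tell tumor from nerve. Suppose a non-VS case has a different cranial nerve against the tumor. The planned outcome data would describe the facial nerve and hearing, but could not show whether the adjacent nerve was spared or injured. That is the patient-level result closest to the study question in such a case.

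This has to be settled in the protocol. An analysis plan can define denominators and subgroups later, but it cannot recover nerve function that was never recorded before surgery and at 3 months.

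**Working it through.** No arithmetic applies. The plan gives no figure for these outcomes, no target rate and no split of the 90 patients by tumor type. The check is a comparison of sections.

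| Element | Section | Adapted to meningioma, HNP, HNS? |
|---|---|---|
| Eligibility | 3.5, 3.6.2, 3.6.5 | Yes, all four types named |
| RGB hypothesis | 3.4 | Yes, may extend to nerves or structures around the other tumors |
| Image capture | 3.5 | Yes, other structures allowed |
| RGB endpoint | 3.6.9, first paragraph | Yes, separate analysis |
| Intraoperative stimulation values | 3.6.11, item 9 | Partly: taken only where relevant, but facial nerve only |
| Survey item 9, facial and hearing rows | Appendix 3 | Partly: N/A may be circled, but no other nerve is listed |
| Clinical outcome objective | 3.1 | No |
| Functional endpoint | 3.6.9, second paragraph | No |
| Preoperative and 3-month data list | 3.6.11, item 12 | No |
| Monitored adverse events | 3.6.10, 7.4.1 | No cranial nerve item for any tumor type |

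1. The three places that determine which nerve function is collected (3.1, 3.6.9 and 3.6.11 item 12) agree with one another. The limitation is therefore not a slip in one sentence.
2. The gross total resection part of the endpoint applies to any tumor type and is unaffected.
3. One row of survey item 9 asks about distinguishing tumor from normal nerve in general. That is the surgeon's rating of helpfulness and does not measure function.
4. Section 7.4.1 also requires any adverse event that is observed or reported to be recorded, and its serious category covers permanent functional impairment. A deficit of another nerve can therefore enter the data. It enters as an event report, without a baseline examination and without a planned 3-month assessment of every patient at risk. Between discharge and the 3-month visit, reporting depends on the patient contacting the team. A systematic rate cannot be formed from such reports.
5. Sections 3.6.7 and 7.2 withdraw patients whose tumor is not VS. Taken literally, they would remove all meningioma, HNP and HNS patients, and the mismatch would disappear. They conflict with 3.5, 3.6.2 and 3.6.5. Section 3.6.7 expects such withdrawals in under 5% of subjects, and 3.5 leaves 95 − 90 = 5 spare places. Both figures fit an occasional unexpected diagnosis better than the removal of three enrolled tumor types.

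**The case against.** **The hypothesis names only facial and hearing function.** This is correct. Section 1.3 speaks of conserving those two functions and of gross total resection, and the endpoint measures exactly these. Adding nerves widens the stated question. But that hypothesis sits in a section that still describes all 90 patients as having suspected VS, so it too was not fully updated when the other tumors were added.

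**The wording is not exhaustive, and adverse events are recorded.** Both the objective and the endpoint use open wording, and 7.4.1 captures observed or reported events. It would therefore be wrong to say that such deficits go unrecorded, or that they surface only when someone volunteers them. What stands is the lack of a dedicated data item and of a planned assessment.

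**Stronger readings that the documents do not support.**
- A reader might infer that facial and hearing nerves not at risk would count as preserved and inflate a pooled rate. The protocol states no preservation category, denominator or pooling rule, and these may sit in an analysis plan that is not shown. Any percentage would rest on an assumed tumor mix and assumed rates, so none is given here.
- A reader might infer that the plan measures the wrong nerve for three of the four tumor types. No section says which nerves are at risk by tumor type, or that the facial and cochlear nerves are safe outside VS surgery. Cranial nerves in general can include those two.
- A reader might infer that hearing results are decided by the translabyrinthine approach named in 3.6.11 and 4.4. The protocol does not describe that approach's effect on hearing.

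**Weight.** This is a secondary endpoint in a largely descriptive feasibility study whose primary endpoint is a surgeon survey. No stated test or decision depends on it. That limits the importance of the point but does not remove it.

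**Conclusion.** The concern holds in a limited form. The functional endpoint was not adapted to the added tumor types. In non-VS cases with another cranial nerve beside the tumor, the plan has no systematic preoperative or 3-month measure of that nerve.

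The number of patients affected cannot be derived. It depends on how many of the 90 have a non-VS tumor and on which nerves lie beside it, and the protocol gives neither. The primary endpoint, the gross total resection rate and the RGB analysis are untouched.

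The conclusion rests on two assumptions: that non-VS patients stay in the study population, as 3.5, 3.6.2 and 3.6.5 indicate, and that at least some of them have an adjacent cranial nerve other than the facial or cochlear, which the general wording of 1.3 allows but does not itemize. The change is worth making before enrolment of these tumor types proceeds, because the missing baseline may not be recoverable afterwards.

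**What to change.** 1. In 3.6.9 and in item 12 of 3.6.11, add function of the cranial nerve(s) adjacent to the tumor for meningioma, HNP and HNS. Align 3.1 with this.
2. Have the surgeon name these nerves on the case form before or at surgery. Fixing them before the outcome is known keeps the denominator from being chosen afterwards.
3. Record their status from the preoperative and 3-month visits already planned.
4. Record the surgical approach.
5. Report facial and hearing outcomes by tumor type, among patients in whom those nerves were recorded as at risk.
6. Reconcile the withdrawal of non-VS patients in 3.6.7 and 7.2 with 3.5, 3.6.2 and 3.6.5.

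**Cost.** Protocol wording and a few case form fields, with no added visit. The protocol does not say whether function of other cranial nerves is routinely examined and charted at the two visits. If it is not, the examination must be added to them. Denominators for the facial and hearing results will be smaller, and results for the less common tumor types will be imprecise.
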